4.3 PRIMARY ENDPOINT(S) ANALYSIS

4.3.1 Definition of endpoint(s)

Primary endpoint is annualized rate of change in eGFR during the placebo-controlled treatment period.

For subjects with age greater than 16 years informed consent or assent for adolescent, the Chronic Kidney Disease Epidemiology Collaboration (CKD-EPI) Creatinine Equation 2021 (1) will be used for calculating eGFR.

For subjects with age 12-16 (both inclusive) informed consent or assent for adolescent, the Schwartz equation (2) will be used.

CKD-EPI Creatinine equation (2021) (1)

$eGFR = 142 \times \min(Scr/\kappa, 1)^\alpha \times \max(Scr/\kappa, 1)^{-1.200} \times 0.9938^{Age} \times 1.012$ [if female], where Scr is serum creatinine in mg/dL, κ is 0.7 for females and 0.9 for males, α is -0.241 for females and -0.302 for males. And unit of age is years, which should be calculated to reflect the age at the time when creatinine is measured. The age = (lab sampling date - inform consent date)/365.25 + Age at inform consent.

Schwartz equation (2009) (2)

$eGFR = 0.413 \times (\text{height}/Scr)$ if body-height is expressed in centimeters OR $41.3 \times (\text{height}/Scr)$ if body-height is expressed in meters, where Scr is standardized creatinine in mg/dL.

4.3.2 Main analytical approach

Annualized rate of change in eGFR (slope of eGFR) during the placebo-controlled treatment period will be compared between lademirsen and placebo using a random coefficient linear mixed effect model which includes time as a continuous variable for Stage 1 and Stage 2 subjects combined.

The model will include eGFR measurements from baseline to end of double blind, placebo-controlled period (48 weeks for Stage 1 subjects, up to 96 weeks for Stage 2 subjects) as response variables, and it will include fix effects of treatment (lademirsen or placebo), screening eGFR stratification factor (≤ 35 mL/min/1.73 m², versus >35 to <60 mL/min/1.73 m², versus ≥ 60 mL/min/1.73 m²), age category (<18 versus ≥ 18 years old), SGLT2 inhibitor treatment (with versus without), time, and treatment-by-time interaction. In addition, it will include random intercept and random slope for time to account for the between subject variability. Time will be treated as a continuous variable based on actual eGFR assessment date relative to the randomization date as defined in [Section 5.2](#) (Derivation of “year” for eGFR slope analysis). An unstructured variance-covariance matrix shared across treatment groups will be used to model the variance-covariance matrix for random intercept and random slope using RANDOM statement in PROC MIXED. The model will be fitted using restricted maximum likelihood. Residual errors are assumed to be independent, normally distributed, with a homogeneous variance.

Difference in estimated least square mean slope of eGFR, corresponding 95% CI, and p-value will be presented.

The primary estimand will be the difference in mean slope of eGFR estimated from baseline to up to 96 weeks during the double-blind treatment period in primary population, regardless of whether or not subjects completed the study period of 48 weeks for Stage 1 subjects or the study period of 96 weeks for Stage 2 subjects (eg, early treatment discontinuation). Those data collected after the study drug discontinuation during the follow up period that is within 48 weeks for Stage 1 subjects or with 96 weeks for Stage 2 subjects since first IMP will be included. However, data collected after kidney transplantation or start of hemodialysis will not be included.

The sample SAS programming code for the analysis model is provided in SAS macro for MMRM part of [Section 5.6](#) and also provided below with stratification factors considered.

[Redacted SAS code block]

[Redacted SAS code block]

[Redacted SAS code block]

[Redacted SAS code block]

4.3.3 Sensitivity analyses

4.3.3.1 Sensitivity analysis to assess the robustness of the variability assumption

To assess the robustness of the variability assumption, annualized rate of change in eGFR (slope of eGFR) during the placebo-controlled treatment period will also be analyzed with the same random coefficient linear mixed effect model as specified in [Section 4.3.2](#), with the exception that R side variance covariance matrix for within subject errors will also be applied (using REPEATED statement in SAS PROC MIXED).

R side variance covariance matrix will first be fitted with unstructured (UN), and if the model does not converge with both Hessian and the G matrix being positive definite, the model will be fit using the covariance matrices of the following order specified by a decreasing number of covariance parameters until convergency is met:

- Heterogeneous Toeplitz (TOEPH)
- Heterogeneous First-order autoregressive (ARH(1))
- Toeplitz (TOEP)
- First-order autoregressive (AR(1))
- Heterogeneous compound symmetry (CSH)
- Compound symmetry (CS)

The first covariance structure yielding convergence will be used in the analysis. When the unstructured covariance matrix is used, the Kenward-Roger approximation (DDFM=KR in SAS PROC MIXED) will be used to estimate the denominator degrees of freedom, otherwise, denominator degrees of freedom will be estimated using the between within method (DDFM=BW in SAS PROC MIXED).

4.3.3.2 Sensitivity analysis to assess the robustness of lademirsen treatment effect using only first year data

To assess the robustness of lademirsen treatment effect using first year data, annualized rate of change in eGFR (slope of eGFR) during the placebo-controlled treatment period will also be analyzed with the same random coefficient linear mixed effect model as specified in [Section 4.3.2](#), but excluding any data collected beyond Week 48 for Stage 2 subjects.

4.3.3.3 Sensitivity analysis using two step linear regression approach

In the two-step linear regression approach to estimate mean eGFR slope, first, each participant's eGFR slope will be estimated separately by regressing the participant's repeated eGFR value on the time variable as defined in [Section 5.2](#) (Derivation of "year" for eGFR slope analysis). Second, the eGFR slopes for all participants calculated in the first step will be treated as the outcome variable and fitted into a different linear regression model.

Specifically, **for the first step**, for each subject from both Stage 1 and 2, a linear regression model will be applied with longitudinal post-baseline eGFR during placebo-control treatment period (48 weeks for Stage 1 subjects, up to 96 weeks for Stage 2 subjects) as dependent variable, and longitudinal visit for each eGFR measurement in unit of year as covariate to estimate the individual participant's eGFR slope at placebo-controlled treatment period.

For the second step, the mean eGFR slope will be estimated in another weighted linear regression model by taking the individual participant's eGFR slope at placebo-controlled treatment period estimated from first step from all subjects from both Stage 1 and 2 as the dependent variable. The model will include covariate of treatment group (lademirsen or placebo), screening eGFR stratification factor, age categories (<18 versus ≥18 years old), and SGLT2 inhibitor treatment at time of screening (versus those without SGLT2 treatment at screening). For each subject, the weight will be the sum of the square of difference in each subject's time to the mean time of the same subject, ie, weight for subject i is as follows:

$w_i = \sum_{j=1}^{n_i} (t_{ij} - \bar{t}_i)^2$, where t_{ij} is the time j for subject i and \bar{t}_i is the mean time for subject, and n_i is the number of time points for subject i .

The summary statistics for mean eGFR slopes estimated at placebo-controlled treatment period, including the estimated LS means and SEs, corresponding 95% CIs, and p-values will be presented by treatment group and difference between treatment groups.

Separately, the summary statistics for eGFR slope during screening period will also be calculated with the similar approach with the exception that screening eGFR stratification factor, age categories (<18 versus ≥18 years old), SGLT2 inhibitor treatment at time of screening (versus those without SGLT2 treatment at screening). will not be included as in the model **at second step**.

For visualization purpose, the individual participant's slope at screening period and the placebo-controlled treatment period will be displayed side by side in spaghetti plots by treatment group.

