1 INTRODUCTION

1.1 STUDY DESIGN

This will be a randomized, double-blind, placebo-controlled, multi-center, Phase 2B study conducted in approximately 130 subjects (including 43 subjects in Stage 1/Cohort 1 and approximately 87 subjects in Stage 2/Cohort 2) with Alport Syndrome.

This study will have two stages:

- Stage 1/Cohort 1 (patients in the ongoing Phase 2 study, randomization completed by the end of December 2021) includes 48-week double-blind, placebo-controlled period followed by 96 weeks open label treatment period with lademirsen and 10 weeks post-treatment follow up period.
- Stage 2/Cohort 2 includes 96-week double-blind, placebo-controlled period followed by 48 weeks open label treatment period with lademirsen and 10 weeks post-treatment follow up period.

For Stage 1, 43 eligible subjects are randomized in a 2:1 ratio to receive every week (QW) subcutaneous (SC) doses of lademirsen 110 mg or placebo for 48 weeks with stratification by screening eGFR (<60 mL/min/1.73 m² versus ≥ 60 mL/min/1.73 m²). At the completion of 48 weeks of double-blind, placebo-controlled treatment, all subjects will be eligible to roll over into a 96 week open-label treatment extension period in which all subjects will receive QW active treatment with lademirsen.

Two interim analyses will be conducted using data from Stage 1:

- [REDACTED]
- [REDACTED]

For Stage 2, an additional 87 eligible subjects will be randomized in a 2:1 ratio to receive every week subcutaneous doses of lademirsen, either 110 mg (adults) or 1.5 mg/kg (adolescents), or placebo for 96 weeks. Stratification by screening eGFR level (≤ 35 mL/min/1.73 m², versus >35 to <60 mL/min/1.73 m², versus ≥ 60 mL/min/1.73 m²), age category (<18 years old versus ≥ 18 years old, and screening SGLT2 inhibitor treatment (with versus without SGLT2 inhibitor treatment) will be performed. At the completion of 96 weeks of double-blind, placebo-controlled treatment, all subjects will be eligible to roll over into a 48-week open-label treatment extension period in which all subjects will receive QW active treatment with lademirsen.

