2 SAMPLE SIZE DETERMINATION

This study has two stages as described in [Section 1.1](#). It also has three interim analyses planned as described in [Section 4.9](#).

- [REDACTED]
- [REDACTED]

With total sample size of 118 (43+75) subjects for the primary efficacy analyses, the study will provide approximately 92.6% (regardless of two interim futility analyses decision) power at either formal interim analysis for efficacy (3rd interim analysis) or final analysis to detect a reduced rate of decline of 5 mL/min/1.73 m²/year (~50% reduction) in eGFR annualized rate under lademirsen treatment, in comparison to placebo.

The power calculations were based on simulations of a frequentist random coefficient linear mixed effect model which is detailed in [Section 4.3.2](#). For the simulation, the following model parameters were obtained from analysis of the ATHENA Natural History Study (OBS16374) data:

- Average linear decline in eGFR of 10 mL/min/1.73 m²/year in placebo arm
- Standard deviation (SD) for the residual error of eGFR of [REDACTED] mL/min/1.73 m² and SD for random effect of slope to be [REDACTED] mL/min/1.73 m²/year
- Uniform enrollment of 1 years for 43 subjects from Stage 1, and uniform enrollment of additional 1.67 years for additional 75 subjects from Stage 2. Also at the time of interim efficacy analyses (3rd interim analysis), all 43 subjects at Stage 1 already completed the 48 weeks double blind treatment period.
- In addition, 10% annual dropout rate overall for both Stage 1 and Stage 2 subjects with exponential distribution for time to dropout was assumed.

[REDACTED]

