5.3 APPENDIX 3 DATA HANDLING CONVENTIONS

For analyses of all the primary, secondary and exploratory endpoints during placebo-controlled treatment period, with the exception for the endpoints only collected at Stage 2, data from both Stage 1 and Stage 2 data will be included for the analyses.

Derivation of "year" for eGFR slope analysis

Year of each eGFR measurement relative to the first IMP injection is calculated as (date of eGFR measurement - the first IMP injection date +1) divided by 365.25. Specially, for the last non-missing eGFR measure collected prior to first IMP injection, it will be coded to year=0.

Missing data handling for eGFR

The primary analysis will include all data collected in Primary Population, regardless of whether or not subjects completed the treatment period. Subjects who prematurely and permanently discontinue study medication will be requested to enter 10 weeks post-treatment follow up period. Data collected during those 10 weeks post-treatment period will be included in the primary analysis up to 48 weeks for Stage 1 data, and up to 96 weeks for Stage 2 data.

All efforts will be made to minimize the amount of missing data. eGFR data is scheduled to be collected at baseline, Week 2, Week 4, and every 4 weeks thereafter. However, if data was not collected at the scheduled visits, every possible effort should be made to collect the data at next possible unscheduled visits, and a corresponding week will also be assigned for those unscheduled visits for analysis purpose. For example, if a subject cannot come for a scheduled visit at Week 16, then an unscheduled visit between Week 16 and Week 20 should be planned, and if this unscheduled visit happens on Week 18, then Week 18 data will be used for the analysis.

Demographic formulas

Age at diagnosis of Alport syndrome is calculated as:

$$(\text{Date of diagnosis of Alport syndrome [yyyy-mm-dd]} - \text{Date of informed consent or assent for adolescent [yyyy-mm-dd]})/365.25 + \text{Age at informed consent or assent for adolescent}$$

Time from diagnosis of Alport syndrome (years) is calculated as:

$$(\text{Date of randomization [yyyy-mm-dd]} - \text{Date of diagnosis of Alport syndrome [yyyy-mm-dd]})/365.25$$

For the dates used in the above calculations, if month is missing, it will be imputed to June; and if the day is missing, it will be imputed to the 15th.

Handling of missing data for categorical variable

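### The two-step slope sensitivity analysis (SAP 4.3.3.3) weights by time spread alone, so its model-based standard error is too small when follow-up lengths differ

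*SAP*

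**What the plan says.** SAP 4.3.3.3 works in two steps. Step one is an ordinary regression for each subject, with "longitudinal post-baseline eGFR during placebo-control treatment period" as the response, covering "48 weeks for Stage 1 subjects, up to 96 weeks for Stage 2 subjects". In step two, "the mean eGFR slope will be estimated in another weighted linear regression model", with treatment, the screening eGFR stratum, age category and SGLT2 inhibitor use as covariates. For the weight, "the weight will be the sum of the square of difference in each" visit time from the subject's own mean, that is, w_i = Σ_j (t_ij − t̄_i)². The section promises LS means, standard errors, 95% confidence intervals and p-values. It describes no variance-component step and no robust standard error.

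The primary model in SAP 4.3.2 is a mixed model, and "it will include random intercept and random slope for time to account for the between subject variability".

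The SAP 2.0 addendum (Section 3) restricts the efficacy methods to Stage 1 and the analysis to key endpoints, and reports no major change of statistical method. It does not say whether the two-step analysis is kept.

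**The concern.** Write τ for the SD of true slopes between subjects and σ for the residual SD. A fitted slope then has variance τ² + σ²/w_i. Weighting by w_i is inverse-variance weighting only if τ = 0, which the primary model does not assume. With τ > 0 and unequal follow-up, the subjects followed longest are overweighted. The usual weighted-regression standard error, which takes the variance to be proportional to 1/w_i, is then too small.

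A sensitivity analysis exists to challenge the primary result. One that rejects a true null hypothesis more often than its stated level, with intervals that are too narrow, gives false reassurance.

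**Working it through.** **The plan's own figure.** The SAP gives no operating characteristic for this analysis. Its 92.6% power (SAP 2) belongs to the primary model and cannot be reproduced, because the variance components, the interim details and the simulation code are redacted. It can only be used to calibrate. With 118 subjects split 2:1 and two-sided 5%, power for a difference of 5 is 92.6% if the average slope SD is 7.52: the standard error is 7.52 × √(1/39.3 + 1/78.7) = 1.47, and 5/1.47 − 1.96 = 1.44. Solving this jointly with the protocol's 75% power (Section 7.2.1: 45 subjects; Section 7.2.5: prior SD 2.22 and the 95% posterior rule) suggests τ of about 6.1-7.0 and σ of about 5.0-6.9. Because that rests on approximations, a wider range is used below.

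**Weights.** From SAP 5.3, "eGFR data is scheduled to be collected at baseline, Week 2, Week 4, and every 4 weeks thereafter", with time in years of 365.25 days. Using post-baseline visits only:
- 48 weeks, 13 visits: Σt² − (Σt)²/n = 10,404 − 314²/13 = 2,819.7 week², or 1.036 year².
- 96 weeks, 25 visits: 78,404 − 1,202²/25 = 20,611.8 week², or 7.571 year².
- Ratio 7.571/1.036 = 7.3.

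SAP 2 gives the size: "With total sample size of 118 (43+75) subjects for the primary efficacy analyses". Before dropout, Stage 1 is 43/118 = 36% of subjects but carries 43 × 1.036/(43 × 1.036 + 75 × 7.571) = 7% of the weight. Under weights 1/(τ² + σ²/w_i) with τ = 6.5 and σ = 5.5, the subject variances are 42.25 + 30.25/1.036 = 71.5 and 42.25 + 30.25/7.571 = 46.2. Stage 1 would then carry (43/71.5)/(43/71.5 + 75/46.2) = 27%.

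**Approximate bias.** The second-step scale is estimated from the scatter of the slopes, with expectation of about τ²·mean(w) + σ². Hence

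true variance / reported variance ≈ [τ²·mean(w²)/mean(w) + σ²] / [τ²·mean(w) + σ²].

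This equals 1 if τ = 0 or if all weights are equal. Without dropout, mean(w) = 5.19 and mean(w²)/mean(w) = 7.10. At τ = 6.5 and σ = 5.5 the ratio is (300.0 + 30.25)/(219.3 + 30.25) = 1.32, so the reported standard error is 1/√1.32 = 0.87 of the true one. Dropout spreads the weights further, to a squared coefficient of variation of 0.52. The floor when σ is negligible is then 1/√1.52 = 0.81.

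**Simulation.** Each scenario has 5,000 null trials, 2:1 allocation (SAP 1.1), 10% annual exponential dropout (SAP 2), one binary stratum as covariate, and two-sided 5%. Simulation error is about 0.3-0.45 points. SE ratio means model-based over true.

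Pooled 43 + 75:

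| τ | σ | SE ratio, SAP rule | Type I, SAP rule | Type I, SAP weights with HC3 | Type I, weights 1/(τ² + σ²/w_i) |
|---|---|---|---|---|---|
| 0 | 5 | 1.00 | 5.5% | 5.4% | 5.5% |
| 2 | 5 | 0.90 | 7.7% | 5.5% | 5.3% |
| 4 | 5 | 0.84 | 9.7% | 5.4% | 5.1% |
| 6.5 | 5.5 | 0.825 | 10.7% | 5.5% | 5.1% |
| 8 | 4 | 0.81 | 11.3% | 5.4% | 5.1% |

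Further runs with τ 2-8 and σ 5-6.5 gave 7.4-11.5%, with the standard error 10-20% too small. The last column uses the true variance components.

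Stage 1 only (43 subjects):
- Equal follow-up, τ = 6.5: SE ratio 1.00, type I error 4.6%.
- 10% dropout only: SE ratio 0.96-0.98, type I error 5.4-6.3%; further runs gave 4.5-5.3%.
- An assumed 40% truncated between Weeks 24 and 48: SE ratio 0.92-1.00, type I error 5.1-7.2% (HC3: 4.7-5.0%). Assuming 19 of 43 truncated gave 5.8-6.9%.

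**The case against.** A reader might infer that the reported standard error ignores between-subject slope variation altogether, or that the weight gives wrong inference whenever slopes vary. The documents do not support this. SAP 4.3.3.3 specifies an ordinary weighted regression with no fixed residual variance, so the estimated scale absorbs τ² on average. If τ² really were missing from the standard error, the SE ratio at τ = 6.5 in the pooled design would be about 0.31 and type I error about 55%, against the 0.825 and 10.7% found. With equal follow-up nothing goes wrong.

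The second objection is scope. No Stage 2 participant was enrolled (addendum, Section 3), so the 48/96-week mix that drives the pooled figures never arose, and the addendum may have dropped this analysis. This stands. What remains in Stage 1 comes from dropout and from subjects who had not had the chance to reach Week 48 (addendum 3.1.1). The documents give no count of such subjects, so both truncation patterns above are assumptions. With dropout only, the effect is close to simulation error.

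Third, the primary model carries a random slope, SAP 4.3.3.2 repeats that model without Stage 2 data after Week 48, and no decision rule in the readable text uses the two-step p-value. This also stands, and it limits the consequence. It does not correct the formula, and nothing in the addendum does.

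**Conclusion.** The concern holds in a limited form. As written in SAP 2.0, the two-step analysis has a weight that conflicts with the plan's own random-slope assumption and a standard error that does not allow for the conflict. In the pooled design the standard error is about 10-20% too small and two-sided type I error about 7-12% at a nominal 5%. The size depends on the redacted SDs (assumed τ 2-8, σ 4-6.5) and disappears as τ approaches 0. Under the addendum the effect is nil to modest, about 5-7%, and only if the analysis is run at all.

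It would be wrong to carry the pooled figures over to the Stage-1-only final analysis, to extend the point to the primary mixed model, or to read it as bias in the treatment estimate. The calculations concern the standard error and p-value of one sensitivity analysis.

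**What to change.** Keep the weights in SAP 4.3.3.3 and state that standard errors, confidence intervals and p-values for the second step will be heteroscedasticity-robust (HC3). This needs no variance components and leaves the point estimate unchanged.

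Alternatively, weight by 1/(τ² + σ²/w_i) with estimated components. This is more efficient: at τ = 6.5 and σ = 5.5 in the pooled design, the SD of the treatment difference falls from 1.663 to 1.493, a variance reduction of 1 − (1.493/1.663)² = 19%. Taking the components from the primary model would, however, tie the check to the model it is meant to test.

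The addendum should also say whether the two-step analysis is still run.

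The cost is a sentence of text and a less favourable sensitivity p-value. At τ = 6.5 and σ = 5.5, HC3 standard errors would be about 1.022/0.825 = 1.24 times those now specified in the pooled design. In Stage 1 the factor is about 1.031/0.965 = 1.07 with dropout only and 1.058/0.942 = 1.12 with the assumed 40% truncation. In these runs HC3 standard errors were themselves 2-6% above the true value, so a little of that widening is conservatism.

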4.3.4 Supplementary analysis (while on treatment estimand)

In this analysis, the same method as in [Section 4.3.2](#) will be used to estimate the difference in mean slope of eGFR estimated during the placebo-control treatment period. However, efficacy assessments obtained after IMP discontinuation or introduction of rescue therapy will not be included. This analysis is corresponding to "while on treatment estimand".

4.4 SECONDARY ENDPOINT(S) ANALYSIS

This section will describe the key secondary efficacy endpoints that will be used for the multiplicity adjustment.

